6.2 Cohort Management

A patient will be considered to have completed treatment with study medications following completion of 7 cycles of treatment and the final assessments at treatment discontinuation. An eligible patient receiving at least 1 dose of the investigational agents, DEC205mAb-NY-ESO-1 fusion protein (CDX-1401) given with adjuvant poly-ICLC with or without INCBO24360, will be considered evaluable for safety. A patient that completes 2 or more cycles of treatment will be eligible for the analysis of immune response. Patients who do not complete the study through Day 29 for reasons other than dose limiting toxicities (DLTs) will be replaced. All patients will be included in the analysis of results.

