6.3 Dose Modification

No dose adjustments during this study are planned for the DEC205mAb-NY-ESO-1 fusion protein (CDX-1401) given with adjuvant poly-ICLC vaccine.

In the event of excessive discomfort, skin breakdown or desquamation, or a Grade 3 treatment-related systemic toxicity following CDX-1401 and poly-ICLC dosing, administration of adjuvant (poly-ICLC) on the subsequent day should be omitted. Provided the toxicity has resolved to Grade 2 or less, the next monthly treatment may be administered as scheduled at a new administration site.

Refer to **Section 11.1** for the Phase I parameters and decisions rules for INCBO24360 dose adjustments.

Dose adjustments for hematological toxicity will be based on the blood counts obtained at baseline and after each 28-day cycle of DEC205mAb-NY-ESO-1 fusion protein (CDX-1401) given with adjuvant poly-ICLC and with or without INCBO24360.

If at least 2/3 or 2/6 DLT's are observed in cohort one, the dose of INCBO24360 will be reduced from 300 mg to 100 mg BID. If at least 2/3 or 2/6 DLT's are observed in Cohort 1, the dose of INCBO24360 will be reduced from 100 mg to 50 mg BID in Cohort 2. The study will continue at this dose level.

Dose modification for INCBO24360 are based on decision rules in **Section 11.1**.

Patients will be withdrawn from the study if they fail to recover to Grade 2, CTCAE Version 4.0, from a treatment-related toxicity within 4 weeks (leading to treatment delay of \geq 4 weeks. For patients that recover in $<$ 4 weeks, when toxicities have resolved to Grade 2 or lower, INCBO24360 may be restarted. In patients that recover from toxicity in less than 4 weeks and who restart therapy, the next treatment cycle will be scheduled for 4 weeks later. Additional cycles will also follow at 4 weeks intervals.

Dose modification for Phase IIB (INCBO24360 cohorts)

When an INCBO24360 toxicity is observed, dose administration may be delayed/interrupted to allow for recovery from toxicity. INCBO24360 may be restarted at a reduced dose of 100 mg. po BID. Please contact the PI for attribution.

Based on the phase I safety review, INCBO24360 300 mg. po BID x 7 cycles has been selected for the phase IIB dose. Dose modification criteria will be defined as any Grade 3 or higher treatment-related (i.e. definitely, probably, or possibly related) toxicity that occurs outside the DLT evaluation period including:

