6.3.1 Definition of Dose-Limiting Toxicity

Patients who do not complete the study through Day 29 for reasons other than dose limiting toxicities (DLTs) will be replaced. All patients will be included in the analysis results.

All AEs (as defined in **Section 9**) will be graded according to the NCI-CTCAE scale Version 4.0. Patients who experience a DLT will not receive any additional treatment (i.e., will be removed from the study and followed until resolution of their toxicity) and will not receive continued treatment even at a reduced dosage of the INCB024360 product. Patients with dose limiting toxicities requiring drug discontinuation (specified below) will be removed from the study (see exception for hypersensitivity reaction). The DLT period will be defined as 28 days after the first dose of vaccine. Late developing toxicities, occurring between Day 29 and Day 183 will be monitored throughout the study and according to the schedule of procedures and observations. Patients may be withdrawn from study even if DLT is due to INCB024360 or sirolimus alone. Safety monitoring will include careful assessment and appropriate reporting of AEs, as well as the construction and implementation of a data and safety-monitoring plan (Auditing, Monitoring, and Inspecting). Medical monitoring will include a regular assessment of the number and type of SAEs. Refer to the stopping rules for this study in **Section 6.3.2**. Any event(s) that might appear to trigger a treatment discontinuation rule or trial stopping rule will be discussed with the FDA review team. For phase IIb dose reductions for INCB024360 will be allowed (see section 6.3)

Management and dose modifications associated with AEs are outlined in **Section 6.3**. Refer to **Section 11** for statistical considerations and additional decision rules.

These events should be deemed to be possibly, probably or definitely related to study drugs. DLT criteria will be defined as any Grade 3 or higher treatment-related (i.e. definitely, probably, or possibly related) toxicity that occurs during the DLT evaluation period, including:

- Febrile neutropenia with standard of care treatment for ≥ 7 days. Growth factors may be used according to American Society of Clinical Oncology guidelines.
- Platelets $\leq 50 \times 10^9/L$
- Grade 3 or greater non-hematologic toxicity
- New onset pulmonary hypertension, interstitial pneumonitis or, CNS bleeding
- Serum bilirubin $> 3.0 \text{ mg/dL}$

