6.7 Treatment Discontinuation

Upon treatment discontinuation all end of study evaluations and tests will be conducted. All patients who discontinue due to an AE must be followed until the event resolves or stabilizes. Appropriate medical care should be provided until signs and symptoms have abated, stabilized, or until abnormal laboratory findings have returned to acceptable or pre-study limits. The final status of the AE will be reported in the patient's medical records and the appropriate eCRF. If patient terminates study participation prior to study completion, all efforts will be made to complete an early termination visit (within approximately 30 days of last dose). Assessment will include physical exam, vital signs and weight, performance status, labs (CBC/diff, CMP, LDH, Coag if on anticoagulants, con med/AE assessment.

Reasons for treatment discontinuation should be classified as follows:

- Death
- Progressive disease
- Treatment-related toxicity
 - Subjects who experience a DLT will not receive any additional treatment (i.e., will be removed from the study and followed until resolution of their toxicity) and will not receive continued treatment even at a reduced dosage of the INCB024360 product.
 - Persistent toxicity that is unresolved to a grade 2 toxicity, where subsequent treatment cannot be given.
- Toxicity unrelated to treatment
- Investigator judgment

- The Investigator may withdraw a patient if, in his/her judgment, it is in the patient's best interest to do so.
- Noncompliance
- Patient voluntary withdrawal
 - A patient may withdraw from the study at any time, for any reason. If a patient discontinues treatment, an attempt should be made to obtain information regarding the reason for withdrawal.
- Roswell Park's decision.

Patients who are unavailable for follow-up evaluations should be classified as lost to follow-up for 1 of the following reasons:

- Lost to follow-up: For a patient to be considered lost to follow-up, the Investigator must make 2 attempts to re-establish contact with the patient. The attempts to re-establish patient contact must be documented (e.g., certified letter).
- Death: Date and cause of death will be recorded for those patients who die within 30 days after last dose of study drug (telephone contact is acceptable).

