Urinary Pregnancy Test in Females of Childbearing Potential	X																							
Concomitant Medications	X ¹²	X			X		X		X		X		X		X		X		X		X			
Adverse Events	X	X			X		X		X		X		X		X		X		X		X			

Study Event	Baseline ¹	Cycle 1			Cycle 2		Cycle 3		Cycle 4		Cycle 5		Cycle 6		Cycle 7		.1.1 Treatment discontinuation ¹³	3 Months, 6 Months, and 12 Months After Last Vaccine or dose of INCB
		Day 1	Day 2	Day 15	Day 1 ± 3 days	Day 2												

- 1 To be performed within 28 days prior to the first vaccination.
- 2 Positive by either PCR or immunohistochemistry ((archived tissue (**Appendix F**) and/or frozen/fresh tumor tissue (**Appendix G**)). Documented historical NY ESO 1 positive results by IHC **or** PCR **or** serum antibody reactive with ESO are acceptable.
- 3 Refer to **Appendix H**
- 4 Including CT scan abdomen and pelvis, or PET/CT as described in **Section 8.5**; within 28 days prior to first vaccination. If patient early terms, CT will be performed at the PI's discretion.
- 5 Only 3 months and 6 month for those patients who have not experienced disease progression.
- 6 Hematology includes: CBC with auto differential, platelets. PT/INR for patients on anticoagulants.
- 7 Chemistry includes: glucose, urea nitrogen, creatinine, calcium, protein, albumin, bilirubin, AST, ALT, LDH, alkaline phosphatase.
- 8 Pharmacokinetic sampling is dependent upon cohort. Refer to **Section 7.7** for details.
- 9 Tumor markers to be obtained as per standard of care.
- 10 INCB024360 will be administered daily for 7 cycles.
- 11 Refer to **Section 7.5**.
- 12 Medications ongoing within 1 week prior to first dose of study drug.
- 13 Approximately 30 days after last study drug, con meds and AE's will be followed. Telephone contact is allowed.

Table 4 Schedule of Procedures/Observations (Exploratory cohort with Sirolimus-Roswell site ONLY)

Study Event	Baseline ¹	Cycle 1				Cycle 2				Cycle 3				Cycle 4				Cycle 5				^{1,2} Treatment discontinuation ¹²	3 Months, 6 Months, and 12 Months After Last Vaccine or dose of Sirolimus
		Day 1	Day 2	Day 15	Day 1 ± 3 days	Day 2	Day 1 ± 3 days	Day 2	Day 1 ± 3 days	Day 2	Day 1 ± 3 days	Day 2	Day 1 ± 3 days	Day 2	Day 1 ± 3 days	Day 2	Day 1 ± 3 days	Day 2	Day 1 ± 3 days	Day 2			
Informed Consent	X																						
Medical History	X	X		X	X		X		X		X		X		X		X		X		X		
Physical Examination, vital signs and weight	X	X		X	X		X		X		X		X		X		X		X		X		
NY-ESO-1, TIL, PD-L1, and/or LAGE-1 Expression in Tumor Tissue²	X																						

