8.3 Non-Target Lesions

All other small lesions (longest diameter < 10 mm or lymph nodes \geq 10 mm to < 15 mm short axis) and non-measurable lesions (i.e., leptomeningeal disease, ascites, pleural or pericardial effusion, inflammatory breast disease, lymphangitic involvement of skin or lung, blastic bone lesions, or abdominal masses / abdominal organomegaly identified by physical exam that is not measurable by imaging) should be identified as non-target lesions and indicated as present in the source documents at baseline. The general location will also be documented on the images drawing a regularly-shaped Region of Interest. Measurements of the non-target lesions will not be performed, but the presence or absence of each should be noted throughout follow-up and evaluation.

Those patients, who have no evidence of disease at the baseline, will be documented as no evidence of disease until progression of disease is documented per RECIST 1.1.

- **Complete Response:** Disappearance of all non-target lesions and normalization of tumor marker level, if applicable. All lymph nodes must be non-pathological in size (< 10 mm short axis).
- **Non-Complete Response/Non-Progressive Disease:** Persistence of 1 or more non-target lesion(s) and/or maintenance of tumor marker level above the upper limits of normal.
- **Progressive Disease:** Appearance of 1 or more new lesions or the unequivocal progression of existing non-target lesions. Although a clear progression of non-target lesions is exceptional, in such circumstances, the opinion of the treating physician should prevail and the progression status should be confirmed at a later time.
 - TUMOR RESPONSE ASSESSMENT BY IRRC – PHASE 2
- Tumor Response will be assessed by the Immune-related response criteria (irRC) as published by Wolchok et al. (68). Response is defined as irCR, irPR or irSD over a period of at least 4 weeks. Disease Control by irRC is defined as irSD or irPR or irCR.

PROGRESSION-FREE SURVIVAL (PFS)

Progression-free survival will be determined for each patient with time origin at the start of the treatment (day 1) until the first occurrence of confirmed progression by irRC or date of death if the patient dies from any causes before progression. Every effort will be made to follow patients for progression after they discontinue the study.

OVERALL SURVIVAL (OS)

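### Toxicity removal is worded as leaving the study, and CT after early termination is discretionary; both conflict with the PFS follow-up that Section 8.3 calls for

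*Combined protocol and SAP*

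**What the plan says.** Three places deal with leaving because of toxicity.

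- Section 6.3.1: a patient with a DLT "will be removed from the study and followed until resolution of their toxicity".
- Section 6.7, in the list of reasons for stopping treatment: "Subjects who experience a DLT will not receive any additional treatment". The same gloss about removal from the study follows.
- Section 6.3: "Patients will be withdrawn from the study if they fail to recover to Grade 2" within 4 weeks of a treatment-related toxicity.

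Two places say what is collected afterwards. The early-termination visit in 6.7 lists examination, vital signs, performance status, laboratory tests, medications and adverse events, but no imaging. Footnote 4 of Table 3 (Section 7.3) says that for a patient who terminates early, "CT will be performed at the PI's discretion".

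On the other side, the PFS paragraph under Section 8.3 runs PFS from day 1 to confirmed irRC progression or death from any cause, and adds: "Every effort will be made to follow patients for progression after they discontinue the study". It says the same for overall survival. Section 6.2 states: "All patients will be included in the analysis of results". Section 11 gives no censoring rule for PFS in patients who are removed or withdrawn.

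Two further statements bear on how often the removal rule operates in Phase IIb: "The DLT period will be defined as 28 days after the first dose of vaccine", and "For phase IIb dose reductions for INCB024360 will be allowed (see section 6.3").

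**The concern.** PFS is the primary endpoint of an open-label comparison of 25 against 25 patients. It needs every patient assessed on the same terms until progression, death or the end of planned follow-up, whether or not treatment continues.

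The toxicity rules use one phrase for two different acts. Read literally, they take the patient off the study and name resolution of the toxicity as the point to which she is followed. The visit list and the CT footnote then give the site nothing that obliges it to image her again. A site could comply with 6.3.1, 6.7 and Table 3 and still leave 8.3 unmet.

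The loss would probably not be even between arms. INCB024360 is the only planned difference between Cohorts 2a and 2b. The vaccine with adjuvant had no DLTs in the 21 patients reported in Section 1.6.1.2, whereas INCB024360 alone had DLTs at 300 and 400 mg BID (Section 1.6.2.4). This is an inference: the DLT definition covers all study drugs, so it applies to both arms. At stake are events that a small trial can ill spare, and ascertainment that depends on arm.

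**Working it through.** **The plan's own figure.** The plan gives no number for this point; the nearest is the power of 0.70 in Section 11.1.1. Inputs there are medians of 8 and 16 months, constant hazards, 25 per arm and up to 5 years of follow-up. Alpha is not stated.

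- Monthly hazards: λ = ln 2 / 8 = 0.0866 and λ/2 = 0.0433.
- Expected events by 60 months: 25 × (1 − e^(−0.0866×60)) = 24.9 and 25 × (1 − e^(−0.0433×60)) = 23.1, together 48.0.
- Schoenfeld power: Φ(√48/2 × ln 2 − 1.96) = 0.67 at two-sided 0.05; with 1.645 in place of 1.96 it is 0.775. The two conventions bracket 0.70, so the figure can be neither confirmed nor faulted.

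**Assumptions for the loss.** None of these is in the documents.

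- A share p of patients, 12% or 20% (3 or 5 of 25), is prone to toxicity. The share is the same in both arms because randomisation balances it. For scale, Section 11.1 calls DLTs rare, but its simulations use DLT probabilities of 0.1, 0.2 and 0.5 for Cohort 1.
- These patients have k times the PFS hazard of the others.
- In 2b all of them are removed and censored at 1 month. In 2a all stay on follow-up.

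**Events lost.** With k = 1 and a true HR of 0.50, the chance that a 2b patient has an event after month 1 and by month 60 is (1 − e^(−0.0433×60)) − (1 − e^(−0.0433)) = 0.926 − 0.042 = 0.883. The loss is 3 × 0.883 = 2.6 or 5 × 0.883 = 4.4 events. Power at two-sided 0.05 goes from 0.67 to Φ(√45.4/2 × ln 2 − 1.96) = 0.65, or Φ(√43.6/2 × ln 2 − 1.96) = 0.63.

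**Shift in the hazard ratio.** Let S₀, f₀ be the at-risk and event functions in 2a, and S₁, f₁ those in 2b. The Cox estimate tends to the θ that solves ∫[f₁ − (f₀ + f₁) θS₁/(θS₁ + S₀)] dt = 0. In 2a, S₀ = (1 − p)e^(−λt) + p e^(−kλt). In 2b with no true effect, S₁ is the same until month 1 and (1 − p)e^(−λt) afterwards.

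| Null case (true HR 1.00) | k = 0.5 | k = 1 | k = 1.5 | k = 2 |
|---|---|---|---|---|
| p = 12% | 1.10 | 1.00 | 0.96 | 0.95 |
| p = 20% | 1.17 | 1.00 | 0.94 | 0.92 |

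Hand check for p = 20%, k = 2. Just after month 1 the toxicity-prone share still at risk in 2a is 0.2e^(−0.173) / (0.2e^(−0.173) + 0.8e^(−0.0866)) = 0.187. The 2a hazard is therefore 1.187λ against λ in 2b, a ratio of 0.84. The ratio is 1 before month 1 and drifts back towards 1 as those patients progress, so an average of 0.92 is reasonable.

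With a true HR of 0.50, the same equation gives 0.46 to 0.48 at k = 1.5 to 2 (0.50 to 0.52 with full follow-up), 0.50 at k = 1, and 0.56 to 0.60 at k = 0.5 (about 0.52 with full follow-up). In simulated trials of 25 + 25 with no effect and k = 2, rejection in favour of INCB024360 (nominal 2.5%) rises from about 3% to between 4% and 5%.

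**A different model.** Suppose instead that the altered prognosis arises only in 2b patients with a DLT. Cutting follow-up at day 28 then moves the HR as follows, where the HR is 0.50 in the other patients.

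- Twice the hazard: 0.52 to 0.50 (10% DLT), 0.55 to 0.50 (1 in 6).
- Same hazard: no shift.
- Half the hazard: 0.46 to 0.50 (10%), 0.45 to 0.49 (1 in 6).

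In the null case at twice the hazard, favourable rejection goes only from 1.9% to 2.9% (10%) or from 1.3% to 2.3% (1 in 6). If these patients keep the 3- and 6-month assessments (a cut at about 6.9 months), the shift with the HR at 0.50 is about half or less: 0.52 to 0.51, and 0.55 to 0.53.

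**The case against.** The strongest reply is that 8.3 already settles the matter. Its sentence on follow-up is specific to PFS and is addressed to patients who have left the study, so it can be read as governing over a parenthesis in a safety section. On that reading, following a DLT patient until the toxicity resolves is a minimum for safety follow-up and not the end of PFS follow-up. Section 6.2 keeps all patients in the analysis, and footnote 5 of Table 3 limits the 3- and 6-month assessments to patients without progression but does not exclude those who had a DLT. The 6.3 withdrawal rule names no end of follow-up at all.

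Much of this stands. A reader might infer that these patients are followed only until their toxicity resolves, so that PFS follow-up is in fact cut short. The word *only* is not in the text, and 8.3 asks for the opposite. A reader might also infer that the hazard ratio tilts towards INCB024360. The direction rests on the removed patients' prognosis, and it reverses if they do better than the rest.

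The rule may also operate rarely in Phase IIb. The DLT window is 28 days, and 6.3 and 6.3.1 allow interruption and dose reduction. Even the larger shifts are small beside sampling error: with 48 events the standard error of the log HR is √(4/48) = 0.29, and the 95% range around 1.00 is e^(±1.96×0.289), or 0.57 to 1.76.

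What the reply does not remove is the operational gap. A best-effort sentence sits against an explicit removal rule, a termination visit without imaging and a discretionary CT. In an open-label trial, discretion over who is scanned is itself a route to arm-dependent ascertainment.

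**Conclusion.** The conflict in the text is real and should be corrected. Sections 6.3, 6.3.1 and 6.7 do not distinguish off treatment from off study, and Table 3 footnote 4 lets the imaging lapse, while 8.3 needs progression follow-up to continue. The consequence is a risk of lost PFS data after toxicity, plausibly greater in Cohort 2b.

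If 3 to 5 of 25 patients in 2b were lost at 1 month, the cost would be about 3 to 4 events and 2 to 4 points of power at equal prognosis. A null HR would read anywhere from about 0.92 to 1.17 as the removed patients' hazard goes from twice to half that of the others. These sizes rest on assumed rates, complete loss at 1 month and no loss in 2a, so they show what the wording permits and do not forecast bias. The case for the change rests on the contradiction and its low cost, not on a presumed direction.

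**What to change.** 1. In 6.3, 6.3.1 and 6.7, replace removal or withdrawal from the study by *removed from study treatment* or *withdrawn from study treatment*.
2. Add that these patients keep the disease assessments scheduled for their arm (at the Cycle 4 Day 1 time, at treatment discontinuation, and at 3 and 6 months), then the progression and survival follow-up of 8.3, unless consent is withdrawn.
3. In Table 3 footnote 4, replace the discretionary CT by the scheduled CT for patients who have not progressed.

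This cannot promise scans up to a PFS event. Scheduled disease assessments end 6 months after the last dose for everyone, and later follow-up depends on 8.3.

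The treatment-stopping rules are not changed. The texts on stopping all treatment after a DLT and on dose reduction in Phase IIb (6.3, 6.3.1, 6.7) contradict each other and must be reconciled by the sponsor. The cost is wording in three sections and one footnote, and scheduled scans for a few patients.

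### Some Section 6.3 wording contradicts the Day 1-28 DLT removal rule, and Table 3 makes the early-termination CT discretionary in an open-label PFS trial

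*Combined protocol and SAP*

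**What the plan says.** **The removal rule.** Section 6.3.1 sets the window: "The DLT period will be defined as 28 days after the first dose of vaccine". A DLT is any Grade 3 or higher toxicity in that window that is at least possibly related to study drug. A patient who has one gets no further treatment and "will not receive continued treatment even at a reduced dosage" of INCB024360. Section 6.7 repeats the rule. Neither section names a phase. Section 6.3.1 makes one exception, for hypersensitivity due to INCB024360 alone, where the vaccine may continue; 6.7 omits it. The rule also reaches the exploratory cohort: "Patients may be withdrawn from study even if DLT is due to INCB024360 or sirolimus alone".

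**Phase IIb reductions.** The same paragraph of 6.3.1 ends by allowing INCB024360 reductions in Phase IIb and refers to 6.3. There the criteria are tied to "toxicity that occurs outside the DLT evaluation period including" a list of events.

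**Continuation wording in 6.3.**
- Vaccine: after a Grade 3 related systemic toxicity has fallen to Grade 2 or less, "the next monthly treatment may be administered as scheduled at a new administration site". No phase or time limit is given.
- General restart: for recovery in under 4 weeks, INCB024360 may resume "when toxicities have resolved to Grade 2 or lower".
- Phase IIb restart: after an interruption for toxicity, INCB024360 "may be restarted at a reduced dose of 100 mg. po BID".
- The creatinine item in the list of events outside the window is described as a DLT.
- Sirolimus: a lower dose may be considered after an unexpected toxicity, with no grade or time stated.

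**Imaging.** The synopsis and Section 8.4 schedule disease assessment at treatment discontinuation, and 6.7 requires all end-of-study tests then. Table 3 footnote 4 leaves the CT to the PI when a patient terminates early.

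**The concern.** Stopping or continuing after a Grade 3 event is a safety instruction. It should give one answer whichever section a site opens. Here an investigator who reads the vaccine paragraph of 6.3 can give the Cycle 2 dose to a patient whom 6.3.1 and 6.7 have taken off treatment. Exposure after an early Grade 3 event would then depend on how a site reads the text.

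The CT wording is a second and separate matter, and it is not confined to DLT patients. Phase IIb is open-label and its primary endpoint is PFS. If the scan at early termination is optional, the decision to look for progression can be influenced by the arm.

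**Working it through.** The plan states no figure on this point, so the main check is a comparison of the text. The arithmetic only gives scale.

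**1. Which reading does the text best support?**
- The DLT rule is mandatory and addressed to patients generally, with no phase named.
- The Phase IIb criteria in 6.3 apply outside the DLT period, which implies that the period still exists in Phase IIb.
- Together these give removal for a DLT in Days 1-28 and INCB024360 reduction for later events.

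**2. Test 6.3 against that reading.** Take a patient with a Grade 3 related systemic toxicity on Day 10 that resolves to Grade 2 by Day 20.
- 6.3.1 and 6.7: this is a DLT, so no further treatment.
- Vaccine paragraph: the toxicity has resolved to Grade 2, so the Cycle 2 vaccine may be given. This is a direct contradiction and applies in either arm.
- General restart sentence: recovery took 10 days, under 4 weeks, so INCB024360 may resume. This contradicts the rule unless it is read as confined to non-DLT events, which it does not say.
- Phase IIb restart sentence: 100 mg BID is permitted on its own wording. Its neighbouring criteria suggest a limit to later events, but the sentence has none.
- Sirolimus sentence: the same problem in the exploratory cohort.
- Creatinine item: a Grade 3 event on, say, Day 60 is called a DLT, although 6.3.1 confines DLTs to the first 28 days. Read literally, an event meant to lead to dose modification would lead to removal.

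**3. Imaging.** The synopsis, 8.4 and 6.7 schedule the assessment at discontinuation. Footnote 4 makes its CT optional for early terminations, and the early-termination visit described in 6.7 lists examination, laboratory tests and adverse-event review but no imaging.

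**4. Scale.** The plan gives no Phase IIb DLT rate. Section 1.6.2.4 describes INCB024360 monotherapy.
- Subjects at 300 mg BID or above: 6 + 11 + 5 + 18 = 40.
- DLTs: 1 at 300 mg, 1 at 400 mg, none mentioned at 500 mg and none at 600 or 700 mg, so 2.
- Rate: 2/40 = 5.0%, Clopper-Pearson 95% CI 0.61% to 16.92%.
- Applied to 25 combination patients: 25 × 0.05 = 1.25, range 25 × 0.0061 = 0.15 to 25 × 0.1692 = 4.23.
- Without the 5 subjects at 500 mg: 2/35 = 5.7% (0.70% to 19.16%), or 1.43 of 25 (0.17 to 4.79).
- Chance of at least one affected patient at 5%: 1 − 0.95^25 = 0.72.

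Section 11.1 uses DLT probabilities of 0.1 and 0.2 in two of its three scenarios for the 300 mg cohort. These would give 2.5 and 5 of 25, with a chance of at least one of 0.93 and 0.996. The third scenario, 0.5, is not carried forward because the Phase I safety review selected 300 mg BID.

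For toxicity from the vaccine itself, Section 1.6.1.2 reports no related Grade 3 or 4 event in 21 patients. The one-sided 95% upper limit is 1 − 0.05^(1/21) = 13.3%.

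**The case against.** The strongest reply is that the protocol is coherent if read as a whole. The DLT rule says what will not happen, while the 6.3 sentences say what may happen. Section 6.7 lists DLT and persistent unresolved toxicity as separate routes off treatment, so the under-4-weeks restart rule can belong to the second. The 100 mg sentence sits in a block whose criteria lie outside the window. In addition, sites must contact the PI about attribution, and any event that might trigger a discontinuation rule goes to the FDA review team. Only two sites are named for stratification.

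Much of this stands. A reader might infer that the protocol leaves open whether DLT removal binds Phase IIb at all. The documents do not support that: the unqualified rule and the outside-window criteria point to removal in Days 1-28. On that reading the two INCB024360 restart sentences are loosely worded, and context can rescue them.

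Context does not rescue the vaccine paragraph. It names a Grade 3 related systemic toxicity and permits the next dose, and no statement of precedence resolves the clash. Contacting the PI settles attribution, and the FDA discussion states no treatment rule. Both make divergence between sites less likely but leave the text unresolved.

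A reader might also infer that patients removed for a DLT drop out of PFS follow-up. They do not, on the text: the PFS definition in Section 8.3 commits to seeking progression after a patient leaves the study, follow-up assessments are scheduled at 3 and 6 months, and 6.2 keeps all patients in the analysis.

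It is fair, too, that the CT footnote applies to any early termination and does not arise from the DLT rule. It is therefore treated here as a separate item.

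**Conclusion.** The point holds in limited form. The intended rule is reasonably clear, but the vaccine paragraph and the creatinine label in 6.3 contradict it, and the INCB024360 restart and sirolimus lower-dose sentences lack the limit that would make them agree with it. Footnote 4 undercuts a disease assessment that the protocol otherwise schedules.

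The DLT wording probably affects few patients: about 1 of 25 in the combination arm, and perhaps 4 or 5 at the upper end. This assumes that a rate from refractory solid tumors, without vaccine and under a DLT definition the protocol does not give, carries over. The vaccine conflict may affect nobody, since 0 of 21 earlier patients had a qualifying event, although those patients had mixed doses and adjuvants and no INCB024360. The sirolimus sentence concerns six patients outside the randomized comparison.

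A reader might infer a loss of power or a biased PFS hazard ratio. Neither is shown; what is shown is an opening for assessment to depend on the known arm. Severity is minor to moderate, resting on patient safety and on even-handed ascertainment of progression.

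**What to change.** 1. In 6.3, limit the vaccine-continuation, INCB024360 restart and reduction, and sirolimus lower-dose sentences to events that are not DLTs, that is, after Day 28 or below DLT grade. Repeat the hypersensitivity exception in 6.7. If the sponsor instead means Phase IIb to be exempt from removal, say so in 6.3.1 and 6.7.
2. Delete the DLT label from the creatinine item in the Phase IIb list in 6.3.
3. In Table 3 footnote 4, remove PI discretion over the early-termination CT in Phase IIb for patients without documented progression. State in 6.3.1 and 6.7 that a DLT patient stops treatment but keeps the follow-up disease assessments already scheduled.

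The cost is a wording amendment and a few scans that the schedule already contains. Item 1 as worded adopts the more conservative reading, so a patient with a Cycle 1 DLT stops treatment. The exemption alternative would keep some of these patients on drug, within the 4-week recovery limit of 6.3 and the Grade 4 pause in 6.3.2.
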